The **purpose** of this study will be to generate the data required to thoroughly validate the ability of plague LFI assay to accurately diagnose human infections with *Y. pestis*. These validation data will eventually be presented to the FDA (along with data from other types of studies not from human subjects) to seek approval for commercial license.

STUDY OBJECTIVE

The objective will be to validate this assay on the capillary blood of humans suspected to have plague.

SPECIFIC AIMS

The specific aims of this study are to enroll up to 300 participants who present clinical signs of illness based on specific inclusion criteria. We will collect two types of blood samples from enrolled participants 1) capillary blood from a finger prick and 2) venous blood. The capillary blood will be used for direct testing on the LFI assay and the venous blood will be used to perform independent validations using FDA approved methods. This study is designed as a correlation study to understand 1) how LFI assay results compare with results from traditional diagnostic methods based on DNA detection methods and bacterial culture isolate and 2) effectiveness of capillary blood to serve as a diagnostic clinical sample as compared with traditional biological samples (venous blood, bubo and sputum). The study is designed to evaluate the outcome of LFI (*SMART™-PRT*, New Horizons Diagnostics Corp.

<https://www.nhdiag.com/index.htm>) and how LFI results correlate with the standard plague diagnostics methods used in Madagascar and two other FDA-approved methods. We are not examining the relationship between the results of the LFI and health outcomes of the participants. Decision of participant's medical treatment is solely based on the clinical judgment of the physician and guidelines set forth by Madagascar National Plague Control Program (PNLP). All participants who are tested by LFI will have received medical treatment prior to the start of the study and the continuation of their medical treatment is guided by PNLN and physician judgment only.

BACKGROUND

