Yersinia pestis, which causes the disease plague, is ecologically established in rodent populations worldwide, including on all continents except Australia and Antarctica. Plague is a rapidly progressing highly feared infectious disease that historically was responsible for the deaths of millions world-wide due to natural outbreaks during three major pandemics. Within the last century, several nation states developed plague as a biological weapon and the US government currently lists *Y. pestis* as a potential bioweapon (1) that could be used against US war fighters. As a natural disease, plague continues to be a threat in modern times with the World Health Organization (WHO) classifying it as a re-emerging infectious disease . Human plague outbreaks occur naturally on an annual basis worldwide with the vast majority of cases (4,5) located in rural remote low-resource settings of Madagascar, an island nation off the east coast of Africa. Madagascar has more human plague cases than any other country in the world. In 2015 alone, WHO reported 85.93% of global cases came from Madagascar (2). Over a five-

year period, there have been more than 3,500 suspected human plague cases in Madagascar ([name] et al., unpubl).

In nature, humans acquire plague by being bitten by fleas carrying *Y. pestis*. The bacterium travels to the nearest lymph node (LN) from the wound site and causes LN swelling, known as a bubo (hence, bubonic plague) within 3-6 days post infection with a 50%-70% mortality rate if untreated. If bubonic plague is not medically treated, it can further progress to infect the lungs (pneumonic plague) for which person to person transmission can ensue. Pneumonic plague, is a rapidly progressing disease (1-3 days) with 100% mortality rate; for this reason, aerosolized *Y. pestis* is of concern as a potential biological weapon. Importantly, there are no licensed vaccines currently available for plague, so antibiotics are the only means to medically defeat this disease. Key to preventing mortality and further transmission in rural settings is the ability to rapidly diagnose at the very early acute phase of the disease. Such a diagnostic assay would need to be highly simple and usable in a low-resource setting to effectively service the human populations most affected (local rural inhabitants and possibly warfighters).

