We plan to enroll up to 300 participants across the entire study which encompasses two plague seasons (Aug 2020-March 2021; Aug 2021-March 2022). We aim to enroll at least 150 participants per plague season but if the opportunity presents to enroll more within the first plague season, then we will proceed to enroll up to 300 participants.

- The **inclusion criteria** for this study
 - Adults 18 to 75 years old (male and female)
 - Be able to receive and give verbal communication
 - Children 5 to 17 years old (vulnerable population)
 - Parents or legal guardian be available to give permission.
 - Parents or legal guardian to consent for children (5-6 years)
 - Identified as a suspect human plague case by the local medical professional

 - Will include at least one of the following symptoms:
 - For bubonic plague: High fever, chills, and/or the presence of a painful bubo
 - For pneumonic plague: High fever, chills, cough for less than 5 days, bloody sputum, and/or chest pains.
 - Patients may be recruited from both plague surveillance program and non-plague surveillance programs.
 - For this study, patients from the plague surveillance program will have higher priority for enrollment than patients from the non-plague surveillance programs.

- The **exclusion criteria** for this study
 - Children under the age of 5 years old
 - Children between the age of 5 years to 17 years without a parent or legal guardian
 - Not compliant with the study procedure (blood sampling)

Adults 18 to 75 years old (male and female), Children 5 to 17 years old with parent or legal guardian, Malagasy nationals across all ethnic groups can participate. This study does not exclude pregnant women but they are not considered vulnerable population because their pregnancy status is not a selection criterion. For this reason, Appendix B is not included in this application.

Participants will initially learn about the study from their physician during their medical consultation. They will then receive an information sheet by the physician who will then be referred to an IPM personnel to receive more information about the study.

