When will recruitment occur? Recruitment will most likely occur during the regular plague season (Aug 2020-April 2021 and Aug 2021-April 2022) when plague activity is high but it can happen any time of the year as sporadic cases can arise outside of the normal season. Local physicians will alert IPM of a suspect plague case at their health center. IPM personnel will be dispatched to this local health center and begin the informing, consenting, and enrolling process.

Where will recruitment take place? The recruitment will take place at the site of regional and local health centers throughout Madagascar where local people seek medical assistance. It is local practice for IPM research personnel to visit these healthcare facilities to provide additional medical assistance (during outbreaks) at the invitation of the local physicians and perform plague investigations to fulfill Malagasy government mandates.

Identifying partnering healthcare centers. During the low plague season (May – Aug), IPM will contact the local physicians from regional health center to inform them of this study. Physicians will learn about the study's purpose, design, and the referral role for which they would serve. From these communications, IPM will know in advance which health centers plan to participate.

Identifying suspect plague case and providing immediate medical treatment. When the local physician has identified a suspect plague case based on clinical presentation, he/she will perform the national protocol for declaring suspect plague case. This includes collecting medical workup samples (sputum and/or bubo aspirates) and completing a TLO declaration form. The sample and TLO form are to be given to IPM for medical workup for official confirmation, irrespective if the patient enrolls in the study. The physician will then provide standard medical care according to PNLP. This includes administration of antibiotics. Blood collection is not part of the standard medical workup.

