Role of physicians as providing referrals. The physician is not part of the research but will provide prospective subjects with information about the research (which, in this case, includes the information section of the informed consent document but will not obtain subjects' consent for the research or act as representatives of the investigators. This practice is in alignment with guidance on engagement described here: <https://www.hhs.gov/ohrp/regulations-and-policy/guidance/guidance-on-engagement-of-institutions/index.html>. After the start of medical

treatment, the local physician will alert the Plague-IPM Unit of suspect plague case(s) at their health center. IPM will immediately dispatch field investigators who will arrive as soon as possible. The physician will give a leaflet to the patient that will provide information about the study conducted by IPM. If the patient is illiterate, then the physician will read the leaflet aloud. The local physician will then refer them to IPM personnel for more information. This is a process approved by the local ethics committee. The physician will not participate in the consenting and enrollment process but rather refer patients to the study. Medical treatment already started before introduction of the study and will continue regardless of study enrollment status.

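### Every finger-prick sample is taken after antibiotics have started and after a delay with no stated limit, yet the validation claim is not restricted to suspects already on treatment

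*Protocol*

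**What the plan says.** **Claim.** The Study Objective reads "The objective will be to validate this assay on the capillary blood of humans suspected to have plague", and the purpose statement before it adds "These validation data will eventually be presented to the FDA". Neither names a phase of illness or restricts the claim to treated patients. The Background gives the need as "the ability to rapidly diagnose at the very early acute phase of the disease".

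**Treatment.** The Specific Aims state: "All participants who are tested by LFI will have received medical treatment prior to the start of the study". The section on identifying a suspect case has the local physician collect sputum or bubo aspirate, and continues: "The physician will then provide standard medical care according to PNLP. This includes administration of antibiotics".

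**Delay.** Under the role of physicians, IPM is alerted once treatment is under way, and then "IPM will immediately dispatch field investigators who will arrive as soon as possible". The same section ends: "Medical treatment already started before introduction of the study and will continue regardless of study enrollment status". The consent section allows two to three hours for the visit. The post-enrollment section provides for one collection of venous and capillary blood.

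**Eligibility.** The symptom criterion is introduced by "Will include at least one of the following symptoms". The only duration limit, cough under 5 days, is one item in the pneumonic list.

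**Analysis.** The statistical section plans a 2 x 2 table of LFI against culture, from which sensitivity is taken, and comparisons with the other tests in Table 3.

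**The concern.** A diagnostic accuracy figure belongs to the patients and the moment at which the sample was taken. Here that moment is after the first antibiotic dose, at an interval set by when the alert is raised and how far IPM must travel. The claim carries no such restriction.

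Two results are at stake. The first is capillary sensitivity, which would be submitted as evidence that the test diagnoses plague. A low figure could mean a weak test or antigen lost under treatment. A high figure could owe something to antigen that built up during the delay. Without recorded times these cannot be told apart. The second is the comparison in the second aim between capillary blood and the traditional specimens. Those are taken before antibiotics and the finger-prick after, so a difference between sample types could equally be an effect of treatment and time.

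**Working it through.** The Protocol gives no expected sensitivity, prevalence, precision target or power for its 300 participants, so there is no stated figure to reproduce. The core of the point is a reading of the text. The arithmetic that follows is illustration on assumed values.

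**1. Order of events.**
- Sputum or bubo aspirate collected by the local physician.
- Antibiotics given by the physician.
- IPM alerted, then staff dispatched.
- Information, consent and enrollment.
- One venous draw and one finger-prick.

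By design, 0% of capillary samples precede treatment. That share stays at 0% for any enrollment up to 300.

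**2. Limits on delay.** None is stated from first dose or from symptom onset. The cough limit does not bind, because a participant can qualify on another listed symptom. Sites are health centers throughout Madagascar, so travel time can be expected to vary.

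**3. Effect of the mix on sensitivity.** Let w be the share of culture-positive cases sampled late. Then overall sensitivity = (1 − w) × Se_short + w × Se_long. With Se_short = 0.90 assumed:

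| Se_long (assumed) | w = 10% | w = 50% | w = 90% |
|---|---|---|---|
| 0.80 | 0.89 | 0.85 | 0.81 |
| 0.70 | 0.88 | 0.80 | 0.72 |
| 0.50 | 0.86 | 0.70 | 0.54 |

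For example, 0.9 × 0.90 + 0.1 × 0.70 = 0.88, and 0.1 × 0.90 + 0.9 × 0.70 = 0.72. If sensitivity rose with delay, the movement would be the other way.

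**4. Effect on the reference.** The venous blood for culture is drawn at the same visit, so culture may lose positives too. Assume 120 infected (40% of 300), 180 not infected, LFI sensitivity 0.80 and specificity 0.98, culture specificity 1, and independent errors. If culture sensitivity is 50%:
- culture-positive = 120 × 0.5 = 60
- culture-negative = 180 + 60 = 240
- LFI-negative among these = 60 × 0.20 + 180 × 0.98 = 188.4
- apparent specificity = 188.4 / 240 = 0.785, against a true 0.98

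With culture sensitivity of 80% or 30%, apparent specificity is 0.89 or 0.73. Under independence, apparent sensitivity stays at 0.80.

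If both tests lose positives with delay, apparent sensitivity is too high. Take 60 infected sampled early (culture 100%, LFI 0.90) and 60 late (culture 30%, LFI 0.70):
- culture-positive = 60 + 18 = 78
- LFI-positive among these = 54 + 12.6 = 66.6
- apparent sensitivity = 66.6 / 78 = 0.85, against 0.80 in all 120 infected

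So the direction cannot be fixed in advance.

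**5. What strata could show.** At a sensitivity of 0.80, the 95% Wilson interval is 0.55 to 0.93 with 15 reference-positive cases, 0.63 to 0.91 with 30, and 0.68 to 0.88 with 60. Detecting 0.90 against 0.70 with 80% power needs 62 cases per stratum. With 15, 30 or 60 per stratum (10%, 20% or 40% of 300 reference-positive, split evenly), power is 27%, 49% or 79%. A split by delay is therefore descriptive.

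**The case against.** The strongest reply has five parts.

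- **The early phase is background motivation.** The formal objective names no phase, and it can be met for treated suspects. This stands: the mismatch lies between the rationale and unrestricted claim on one side and the sampled population on the other. The design does not fail its objective.
- **Prior treatment is disclosed in the Specific Aims.** True, but it appears there to separate the study from clinical care. It is not carried into the purpose or objective as a limit on the claim.
- **An analysis plan may stratify, and data forms are not shown.** Fair, so the absence of strata is not held against the Protocol. But no analysis can supply capillary samples from before treatment or use times that were not captured. The consent section lists medical treatment among the data and does not name the time of first dose.
- **The calculations rest on assumed values, and patients cleared of bacteria tend to leave the sensitivity denominator.** Both stand. The Protocol gives no data on how antibiotics or delay change either antigen in capillary blood, and its assay description says LcrV behaviour in human infection is unknown.
- **Treating first follows national guidance and is outside the research.** Not disputed. Nothing here touches it.

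A reader might also infer more than the text supports:

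- *That every LFI result is post-treatment, or that nobody is sampled at first contact.* The LFI is also run on residual bubo aspirate and sputum collected before antibiotics. These are a different sample type and cannot stand in for the finger-prick.
- *That the Background requires testing before treatment decisions.* It does not say so.
- *That patients reached by IPM are later or milder cases.* This is plausible given the 1-3 day pneumonic course in the Background, but that course is not shown to apply to treated patients, and no travel time is given.

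**Conclusion.** The point holds for capillary blood. All finger-prick LFI results come from suspects already on antibiotics, sampled once, at an uncontrolled and possibly unrecorded interval. Capillary accuracy before treatment cannot be estimated directly, and the sensitivity against culture is specific to whatever mix of delays occurs. The comparison of capillary blood with bubo aspirate or sputum confounds sample type with treatment and time.

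This rests on the Protocol's own order of events. The size and direction of any error do not follow from it. The range 0.88 to 0.72 is one assumed case, and joint loss of LFI and culture positives would instead push apparent sensitivity up. The stronger conclusion, that the study will understate or overstate accuracy by a known amount, is not supported. The matter should be settled before enrollment, because times not taken at the visit may not be recoverable.

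**What to change.** No change to patient care is implied.

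1. Make four times required data items: symptom onset, first antibiotic dose, bubo or sputum collection, and finger-prick.
2. Keep the overall capillary estimate. Add capillary LFI accuracy with confidence intervals by time since first dose and by clinical form, labelled descriptive. Do not promote a short-delay group, such as the first 24 hours, to the headline: the cut would be arbitrary, the group small, and its members still treated.
3. When comparing capillary blood with bubo aspirate or sputum, report the interval between the paired samples and say that sample type and treatment cannot be separated.
4. State in the objective and conclusion that capillary accuracy is validated in suspects already on treatment, and that performance before treatment is an extrapolation. Reconcile the Background rationale with this.

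Cost: two to four extra fields, depending on what existing forms already hold; small strata with wide intervals; and a narrower claim for the submission.
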